### 4.2 Exclusion criteria

1. Pregnancy
2. On-going participation in any investigational research which could undermine the scientific basis of the study
3. Presence of any of the American Thoracic Society's contraindications to exercise testing (Appendix 1)
4. Previous intermediate/high risk surgery within three months prior to recruitment
5. Previous participation in the VERVE study at any time
6. Presence of cardiac pacemaker or implantable cardioverter-defibrillator.

### 4.2.1 Rationale for inclusion/exclusion criteria

Aging is a cardiovascular risk factor. Previous studies have identified patients over 65 years or age over 40-45 years with one peri-operative risk factor as at increased risk of post-operative cardiovascular events. Proportionally, the majority of patients undergoing high risk surgery are aged over 59 years so including patients over 50 years of age should allow for a

cohort at increased risk of peri-operative myocardial injury whilst ensuring a degree of generalisability within non-cardiac surgery patients.

Although incorporating orthostatic heart rate recovery into the protocol, our main intervention relies on patient's being able to step well enough to generate a heart rate response of approximately 60% predicted maximum heart rate (HRmax). This criterion will also therefore exclude a proportion of patients whose mobility may be limited by musculoskeletal problems rather than impaired cardiovascular fitness. The presence of a cardiac pacemaker may alter the heart response to exercise and recovery; an implantable cardioverter-defibrillator (ICD) may be stimulated if the patient heart rate exceeds that which is expected.

The prevalence of post-operative myocardial injury after low risk surgery is low, and so may be a difficult signal to identify. Low risk surgery is often performed as day-case and so post-operative monitoring is difficult in this cohort. In order to facilitate generalisability of the measure, patients undergoing intermediate/high risk surgery as defined by the ESC/ESA i.e. >1% risk of cardiovascular death or myocardial infarction will be recruited. Identifying patients by surgical risk rather than individual patient risk should allow a wide variety and degree of co-morbidity.

#### **4.3 Withdrawals and exclusions**

A patient may request withdrawal from the study at any time without it affecting their clinical care. The patient will not have to give a reason for their decision to withdraw.

Participants will be made aware from the beginning of their participation in the study that they can freely withdraw (discontinue participation) from the study (or part of) at any time. The sample size calculation allows for participant withdrawal of approximately 5%, so it is not anticipated that it will be necessary to replace participants who withdraw. The situation will be monitored throughout the study by the Chief Investigator.

Types of withdrawal will be collected on a "Change of Status Form" defined as:

- The participant would like to withdraw from the study but is willing to be remotely followed up in accordance with the schedule of assessments (i.e. the participant has agreed that data from medical notes can be collected and used in the study analysis but they do not want to be contacted via telephone for questionnaires from that point onwards).
- The participant would like to withdraw from the study and is not willing to be followed up in any way for the purposes of the study and for no further data to be collected (i.e. only data collected prior to the withdrawal can be used in the study analysis).
- The participant wishes to withdraw completely from the study and all study follow up, and is not willing to have any of their data, including that already collected, to be used in any future analysis.

The details of withdrawal (date, reason and type of withdrawal) will be clearly documented in the source data and on the "Change of Status Form".

All patients will be consented pre-operatively, but can withdraw consent at any time. Patients undergoing some high risk procedures e.g. elective AAA repair may be admitted to Intensive Care post-operatively, and may be sedated for longer than one post-operative day. This will be explicitly clarified with the patient pre-operatively, and confirmed that troponin levels and post-operative complication data will still be collected and recorded if they are unconscious. However, the day 2 QoR-15 scale will not be performed. If sedation is required for longer, the

patient-centred secondary outcomes may not be completed but we envisage this will be a minority of patients. All other post-operative complication and clinical indicator data will be collected from notes reviews.

## 5. **Study Conduct**

### 5.1 **Recruitment**

Each recruiting hospital and surgical specialty has its own referral pathway from surgical outpatient clinic and diagnosis through to pre-assessment and admission for surgery. Therefore each pathway will vary, but in general we will aim to identify patients as early as possible in their pathway either via surgical referral or pre-assessment clinic. Eligible patients will ideally speak with a member of the research team face to face and take the Participant Information Sheet home to consider and discuss with others. Due to the rapid turnaround of surgical referrals to surgery however, some patients may receive a cover letter and Patient Information sheet in the post with the paperwork about their procedure. This will allow for telephone discussion prior to consent. We will aim to consent and collect all pre-operative data, including performing the submaximal exercise test at pre-assessment clinic or on the ward if the patient is admitted prior to the day of surgery. Exercise testing will not be performed on the day of surgery.

### 5.2 **Consent**

Written informed consent will be obtained following a face-to-face discussion about the study. Prior to obtaining consent, patients will have received a Patient Information Sheet and allowed at least 24 hours contemplation time before consenting to participate and performance of the exercise test. The research team will endeavour to ensure understanding including study procedures, risks, benefits and the patient's right to withdraw.

### 5.3 **Data collection**

Data collection involves:

- Baseline demographic data
- Laboratory sampling
- Pre-operative questionnaires
- Pre-operative risk scores
- Post-operative clinical data
- Post-operative questionnaires

All clinical data will be collected locally and case report forms (CRFs) completed by study staff. The data will be anonymised at site and a unique alphanumeric study number allocated. The study will adhere to data protection regulations. Patients' identities will be protected and their information held securely.

#### 5.3.1 **Baseline demographic data**

Case note review and routine pre-operative investigations:

- Age
- Sex
- Ethnicity
- Height and weight
- Operation
- Indication for operation
- Alcohol consumption (units/week)
- Smoking history (current and pack years; time since abstinence if applicable)
- Metabolic equivalents

- American Society of Anaesthesiology score
- Clinical Frailty Score
- Co-morbidity (including history of Covid-19 infection)
- Drug history, including medication taken on day of test
- Routine observations (blood pressure, oxygen saturations, respiratory rate)
- Pre-operative ECG finding
- Consultant Anaesthetist caring for the patient on the day of surgery's perception of peri-operative risk as per their routine risk assessment

### 5.3.2 Laboratory sampling

- Pre-operative NT-proBNP
- High-sensitivity troponin assay (as per the NHS clinical laboratory of each recruiting centre): pre-operatively and days one and two post-operatively. These will be drawn contemporaneously with routine bloods.

### 5.3.3 Pre-operative questionnaires (Full details in Appendix 2)

- Quality of Recovery-15 scale (QoR-15): a validated evaluation of the quality of post-operative recovery. It will be performed pre-operatively for baseline score.
- EQ-5D-5L: EuroQol health-related quality of life scale
- Patient perception of submaximal versus maximal exercise testing in CPET cohort

### 5.3.4 Pre-operative risk scores

- Duke Activity Scale Index: brief self-reported functional capacity scale (Appendix 2).
- Revised Cardiac Risk Index: commonly used risk score for cardiovascular complications after major elective noncardiac surgery.
- Surgical Outcome Risk Tool: commonly used risk stratification tool predicting 30 day mortality after non-cardiac surgery.
- P-POSSUM/V-POSSUM: pre-operative risk scores incorporating physiology and surgical domains, predicting post-operative morbidity and mortality.
- All pre-operative risk scores will be completed by study investigators, blinded to clinical team. It is permissible for clinical teams to use risk scores as per their usual practice.

### 5.3.5 Post-operative clinical data (Full details in Appendix 3)

- Acute Kidney Injury (AKI) as defined by KDIGO consensus at day 7. If urine output is no longer recorded (as not perceived to be clinically necessary), AKI will be scored by serum creatinine only.
- Major Adverse Kidney Events (MAKE) at day 30. MAKE is a composite of ≥30% decline in eGFR at baseline, renal replacement therapy of any duration and renal mortality.
- Infective complications at day 7. These will include presence of fever >38.5°C more than 24 hours following surgery; non-prophylactic antibiotic use and documentation of suspected site (chest/urinary/blood/wound/other). Adapted from StEP-COMPAC outcomes for infection and sepsis.
- Cardiovascular complications at day 7. As per StEP-COMPAC, these include myocardial infarction, cardiovascular death, non-fatal cardiac arrest, coronary revascularisation, PE/DVT and new-onset of atrial fibrillation.
- Major adverse Cardiac Events (MACE) at day 30, day 90 and at 1 year. MACE is a composite of myocardial infarction, non-fatal cardiac arrest, coronary revascularisation and cardiac death.

- Pulmonary complications at day 7, encompassing atelectasis, pneumonia, acute respiratory distress syndrome (ARDS, as defined by Berlin criteria) and pulmonary aspiration.
- Neurological complications at day 7 including 4AT score, and use of anti-delirium medications.
- Admission to ICU at day 14 (or re-admission)
- Days alive and out of hospital at day 30: validated patient-centred outcome that reflects mortality, length of hospital stay, readmissions and discharge to another health facility other than the patient's home.
- All-cause mortality at day 30, 90 and 1 year
- Length of hospital stay +/- in-hospital mortality

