### 1.8 Rationale

Effective pre-operative functional capacity testing is part of the evolving peri-operative care pathway which aims to involve patients and their families in integrated and shared decision making to improve patient experience and outcome, and also cost-effectiveness of the surgical pathway within the NHS. Heart rate recovery after submaximal exercise testing offers a widely available and economical additional way to identify high risk patients in order to discuss risk with patients and to allocate resources correctly e.g. elective post-operative critical care. This is the first study seeking to validate submaximal HRR in an intermediate/high risk surgical population.

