#### **3.2 Secondary outcome measures**

- Post-operative complications at day 7 based on and including StEP-COMPAC cardiovascular complications, post-operative pulmonary complications, infection, cognitive dysfunction, and acute kidney injury.
- Composite outcomes: major adverse cardiac events (MACE) and major adverse kidney events (MAKE) at days 7 and 30

- Patient-centred outcomes: quality of recovery scale 15 (QoR-15), EQ-5D-5L score, days alive and out of hospital (DAOH) at day 30 and after 1 year
- Clinical indicators: mortality at day 30 and after 1 year, admission to ICU at day 14, readmission to hospital at day 30 and length of hospital stay (with/without in-hospital mortality)
- CPET sub-study: comparison of maximal and submaximal heart rate recovery, plus HRR versus CPET derived indices (AT, VO2peak, and VE/VCO2 at AT). We will also examine patients' perceptions of both tests.

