## 4. Selection and withdrawal of study participants

### 4.1 Inclusion criteria

1. Provision of informed consent
2. Age >50 years
3. Able to walk unaided
4. Planned elective intermediate/high risk surgery as defined by European Society of Cardiology/European Society of Anaesthesiology (ESC/ESA) guidelines (Table 3)

Table 3 Reproduced from ESC/ESA non-cardiac surgery guidelines

Low-risk: < 1%	Intermediate-risk: 1-5%	High-risk: > 5%

 
• Superficial surgery
 
• Breast
 
• Dental
 
• Endocrine: thyroid
 
• Eye
 
• Reconstructive
 
• Carotid asymptomatic (CEA or CAS)
 
• Gynaecology: minor
 
• Orthopaedic: minor (meniscectomy)
 
• Urological: minor (transurethral resection of the prostate)
 
	
 
• Intraperitoneal: splenectomy, hiatal hernia repair, cholecystectomy
 
• Carotid symptomatic (CEA or CAS)
 
• Peripheral arterial angioplasty
 
• Endovascular aneurysm repair
 
• Head and neck surgery
 
• Neurological or orthopaedic: major (hip and spine surgery)
 
• Urological or gynaecological: major
 
• Renal transplant
 
• Intra-thoracic: non-major
 
	
 
• Aortic and major vascular surgery
 
• Open lower limb revascularization or amputation or thromboemboectomy
 
• Duodeno-pancreatic surgery
 
• Liver resection, bile duct surgery
 
• Oesophagectomy
 
• Repair of perforated bowel
 
• Adrenal resection
 
• Total cystectomy
 
• Pneumonectomy
 
• Pulmonary or liver transplant
 

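### The ICU-admission outcome does not separate planned from unplanned stays, so it partly reflects the operation and pre-operative risk judgement

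*Combined protocol and SAP*

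**What the plan says.** Section 3.2 lists among the clinical indicators "admission to ICU at day 14, readmission to hospital at day 30". Section 5.3.5 gives the version to be collected: "Admission to ICU at day 14 (or re-admission". That section refers to Appendix 3 for details, but Appendix 3 does not define the ICU outcome.

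Section 4.3, on withdrawal and consent, states: "Patients undergoing some high risk procedures e.g. elective AAA repair may be admitted to Intensive Care post-operatively". It adds that this will be explained to the patient before surgery. The procedure class is eligible: Table 3 in section 4.1 lists "Aortic and major vascular surgery" in the high-risk column. Section 1.8 says that HRR could help to identify high-risk patients and "allocate resources correctly e.g. elective post-operative critical care".

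On analysis, section 7.3 promises only appropriate methods for secondary outcomes. Section 7 says that a formal statistical analysis plan will be agreed before any data are analysed.

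**The concern.** An ICU stay expected before the operation and an ICU admission after a patient deteriorates are different events, but the outcome scores them alike. An uncomplicated AAA repair that goes to ICU as foreseen is an event. A ward patient who recovers equally well is not.

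This matters because of what the outcome is meant to show. Table 1 defines predictive validity as identifying patients with poor post-operative outcomes, and places agreement with existing pre-operative risk predictors under construct validity. An expected ICU stay belongs nearer the second. If it depends on the operation or on unit practice, it adds events unrelated to HRR and dilutes any real association. If it depends on the team's view of fitness, HRR may be associated with it because both reflect functional capacity before surgery. Section 1.2 describes pre-operative risk assessment as resting mainly on functional capacity, and sections 1.3 and 1.5 present HRR as a marker of it. The direction of the distortion cannot be known in advance, and without a planned/unplanned field it could not be examined in the study data.

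**Working it through.** **The plan's own figure.** The only sample-size figure is for myocardial injury (section 7.1): AUROC 0.7 against 0.5, 24.5% incidence, type 1 error 0.05, power 80%. With the Hanley–McNeil variance and a two-sided test, 22 cases and 68 controls are needed, 90 in all. With 5% dropout, 90/0.95 = 94.7, rounded up to 95. Both stated figures reproduce. They do not concern ICU admission, for which the plan gives no figure.

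**Reading the definition.** The words at day 14 could mean any ICU admission within 14 days or being in ICU on that day. The mention of re-admission in section 5.3.5 favours the first, because it counts entries to ICU over a period. On that reading expected stays count. On the second, short planned stays drop out, but so do short unplanned ones.

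**Illustration of size.** All rates here are assumptions.

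- N = 90 evaluable patients.
- u = proportion with unplanned admission, 3% to 10%.
- q = proportion with planned admission, 5% to 50%, independent of unplanned need.
- Proportion with any admission: E = u + (1 − u)q.
- Planned-only share of events = (1 − u)q / E.
- Case A, dilution: HRR has AUROC 0.70 for unplanned admission and 0.50 for planned-only admission. AUROC for any admission = 0.50 + 0.20 × u/E.
- Case B, selection: HRR has AUROC 0.70 for planned admission and carries no information on unplanned admission. AUROC for any admission = 0.50 + 0.20 × q/E.

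| u | q | E | Events in 90 | Planned-only share | Case A | Case B |
|---|---|---|---|---|---|---|
| 10% | 5% | 0.145 | 13.1 | 0.045/0.145 = 31% | 0.638 | 0.569 |
| 10% | 10% | 0.190 | 17.1 | 0.090/0.190 = 47% | 0.605 | 0.605 |
| 3% | 10% | 0.127 | 11.4 | 0.097/0.127 = 76% | 0.547 | 0.657 |
| 3% | 50% | 0.515 | 46.4 | 0.485/0.515 = 94% | 0.512 | 0.694 |

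Planned-only stays are the majority of events only when q exceeds u/(1 − u). That threshold is 0.03/0.97 = 3.1% when u = 3%, and 0.10/0.90 = 11.1% when u = 10%. The documents do not say on which side of it this cohort lies.

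The second row shows the difficulty of interpretation. An observed AUROC of 0.605 fits a test that predicts deterioration and is diluted by planned stays. It fits equally well a test that predicts no deterioration and only tracks who was given a planned bed.

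**The case against.** A reader might infer that the outcome mostly records booked ICU beds. The documents do not support that. They give no ICU rate, case mix or booking policy. Section 4.3 speaks only of some procedures after which patients may go to ICU, and many eligible operations in Table 3 are intermediate risk. Section 1.8 describes a prospective use of HRR; it does not describe how the four centres allocate beds now. A reader might also infer that a spurious association with HRR is bound to appear. It could, but only if planned admission tracks fitness; if operation type or unit practice drives it, the effect is dilution.

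The plan has partial safeguards. Clinicians are blinded to HRR (section 2.3). Operation type is recorded, as is the consultant anaesthetist's "perception of peri-operative risk as per their routine risk assessment" (section 5.3.1). Clavien–Dindo grade IV ties critical care to a complication. Section 3.2.1 aligns the secondary outcomes with StEP-COMPAC endpoints for comparison between studies, so replacing the outcome outright could cost comparability.

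The uncertainty about size stands, and so does the comparability point. The safeguards do not change how a planned stay is scored. Blinding to HRR does not stop clinicians judging fitness by other means: section 5.3.4 says "It is permissible for clinical teams to use risk scores as per their usual practice", CPET is routine for a cohort at two centres, and section 5.5 lets the investigator pass on concerns about fitness. Clavien–Dindo grades reported complications and leaves the separate ICU indicator as it is. Operation type and perceived risk allow some adjustment, but do not show which admissions were planned.

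**Conclusion.** The point holds for one secondary outcome. The definition does not distinguish a planned ICU stay from an unplanned one, and the protocol itself foresees ICU after some eligible elective operations. On the cumulative reading, the outcome partly reflects operation type and pre-operative risk judgement, and an association with HRR would be weak evidence of predictive validity. That conclusion needs no assumed rate.

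The size does. The planned-only share is about 31% to 94% across the assumed rates, and could be lower if planned ICU use is rarer than 5%. Whether the net effect is dilution or apparent prediction through clinicians' selection cannot be settled from the documents. The myocardial injury analysis and the sample size of 95 are untouched.

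**What to change.** In sections 3.2 and 5.3.5, state the window as within 14 days of surgery and make the Table 2 row and Appendix 3 agree. Add a CRF field recording, for each ICU admission, whether it was planned before surgery. In the analysis plan still to be written, name unplanned ICU admission or ICU re-admission within 14 days as the outcome for HRR prediction, and report any ICU admission alongside it for comparability.

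The cost is one CRF field, a short definition and fewer events. At the assumed unplanned rates, 90 patients would yield 90 × 0.03 = 2.7 to 90 × 0.10 = 9 patients with unplanned admission, well below the 22 cases behind the primary calculation. The result should therefore be presented as an estimate with a wide interval. If the field is not collected prospectively, recovering it means returning to the notes.

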#### **5.3.6 Post-operative questionnaires**

- QoR-15 at day 2.
- EQ-5D-5L at day 90 and 1 year.

### **5.4 Exercise Protocol**

Patients will begin at rest, sitting on a chair. Heart rate will be recorded via one-lead ECG (Actiheart, CamNTech, Cambridge, UK). The ECG leads will remain in situ throughout the test and HR monitored by the investigator throughout. The participant will not be able to see their HR. To ensure baseline heart rate is accurate patients will sit still, without talking, for 5 minutes. Baseline HR will be noted.

#### **5.4.1 Orthostatic HRR**

The initial test will be orthostatic heart rate recovery. Patients will be asked to stand promptly, remain standing for three minutes and then to sit back down, until their heart rate is back to baseline.

#### **5.4.2 Step test**

Prior to the exercise, the patients' age-predicted maximum heart rate will be calculated:

$$\text{Age predicted HR}_{\text{max}} = (208 - 0.7 \times \text{age})$$

The aim of the test will be for the patient to repetitively step onto and off a low box until they reach 60% predicted  $\text{HR}_{\text{max}}$  +/- 5% or the point of subjective limitation. Participants will be encouraged throughout to place alternate feet onto the top of the box, stand erect at the top of the box and place both feet fully on the ground at the end of the stepping "cycle". Standard phrases of encouragement will be used in a neutral tone. Once the HR is approximately 60% predicted  $\text{HR}_{\text{max}}$ , the patients will maintain the effort for a further minute. At the end of the minute, patients will sit and rest. Heart rate will continue to be monitored for a further 5 minutes. A modified Borg score will be assessed at the beginning and end of the test as an indication of perceived workload. The step test also allows an estimate of work done to be calculated:

$$\text{Work done (J)} = \text{mass (kg)} \times \text{height of step (m)} \times 9.8 \text{ (gravity)} \times \text{total number of step cycles}$$

During the test, patients will be asked not to speak as this has been demonstrated to raise heart rate.

